TUFTS MEDICAL CENTER/TUFTS UNIVERSITY RESEARCH PROTOCOL

Version date: 07/23/2018

ClinicalTrials.gov ID NCT02811445

Study Title: Role of the gut microbiome and the serum metabolome on lean mass and physical function in older adults

Principal Investigator: [name]

Co-Investigator: [name].
[name].

Study Doctor/Co-Investigator: [name].

Study Coordinators: [name]
[name]

I. Research Plan

40 older adults (70-85y) will be recruited from the local Boston area based on their performance on the short physical performance battery (SPPB), a measure of lower extremity physical function that includes standing balance, a 4-m walk and chair stand tests^[1]. The SPPB has been extensively validated as predictive of future disability risk and mortality in older adults^[1]. High-functioning (HF; SPPB ≥ 11) and low-functioning (LF; SPPB ≤ 8)^[2] groups will each contain 20 subjects (10 men, 10 women). Gut microbial composition is affected by age^[3, 4]. Similarly, sex and BMI are associated with gut microbiome composition^[5-7]. With the goal of minimizing gut microbial variability, I propose to recruit HF and LF subjects that are matched for age, sex and BMI but are different in terms of lean mass and physical function.

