At baseline, subjects will provide a blood and stool sample that will be subjected to serum metabolomics and fecal sample 16S ribosomal RNA (16S rRNA) gene profiling, respectively. Serum metabolomics provides an analytical description of complex biological media by identifying a large number of small molecule metabolites in a given biological sample^[8]. Fecal sample 16S rRNA gene profiling will be used to identify the bacterial relative abundance that is present within each taxonomic level in each fecal sample. Lean mass and physical function will be measured in all subjects. Associations between serum metabolites, fecal bacteria, and between fecal bacteria and serum metabolites with the differentiation of HF from LF, and that are associated with lean mass and specific measures of physical function will be determined. In addition, associations between gut bacteria with circulating markers of insulin resistance and endotoxemia will be identified. Overlapping associations between gut bacteria and serum metabolites with these outcomes is expected to provide an enhanced understanding about the role of gut bacteria on mechanisms that underlie the maintenance of lean mass and physical function in older adults. The causative role of gut bacteria on the maintenance of lean mass and physical function in older adults will be examined by transplanting fecal bacteria from older adults into germ-free mice.

After 1 month, to determine the reproducibility of the baseline gut bacterial associations with lean mass and physical function, study subjects will return to provide a fecal sample that will be subjected to 16S rRNA profiling. Lean mass and physical function will be measured, and associations between fecal bacteria that collectively differentiate HF from LF, and that are associated with lean mass and specific measures of physical function will be identified and compared with baseline findings.

Statistical power: Sample size estimates are based on gut bacterial associations with the GFI^[9]. Means \pm SD for *Bacteroides/Prevotella* of 26.3 ± 13.2 and 14.8 ± 15.1 in the low-frailty and high-frailty groups, respectively, yield an effect size of 0.81, a value that is sufficient to obtain 80% power at a type-I error probability of 0.05 with a study sample size of 40 subjects. To achieve this recruitment goal, up to 150 subjects will sign the Preadmission ICF, with the goal of 40 participants completing the study.

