Bacterial taxa that differentiate HF from LF older adults: Principal co-ordinate analysis (PCoA) of the phylogeny based Unifrac distance metric^[32], which are derived from OTUs^[33] will be used to determine if the overall gut microbial profile in HF is significantly different when compared with LF older adults. The analysis of similarities function in the statistical software package PRIMER 6 (PRIMER-E Ltd., Lutton, UK^[34]) will be used to determine between-group statistical significance ($p \leq 0.05$). To identify bacterial taxa and relative abundance that are significantly different in HF when compared with LF older adults, linear discriminant analysis effect size (LEFSE)^[35] will be used. LEFSE is an algorithm for high-dimensional biomarker discovery and explanation that identifies bacterial taxa that characterize the difference between two or more biological conditions.

Test the causative role of human gut bacteria on the maintenance of lean mass and physical function: Although identification of gut bacteria that are associated with lean mass and physical function is an important observation, transplanting intact uncultured human fecal microbiota into recipient germ-free mice permits the donors' communities to be replicated and the causative role of their microbiota on outcome measures to be

discerned. For example, transplantation of human gut microbiota from 4 female twins discordant for kwashiorkor (the condition caused by severe dietary protein deficiency) into germ-free mice resulted in 86-90% of species-level taxa and ~90% of the functions encoded by the donor's microbiome being found in recipient mice, thereby implicating the gut microbiota as a causal factor on kwashiorkor^[36].

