A weight (10% of body weight) will be attached to the tail of a mouse, which is then placed in the water. The amount of time that the mouse is able to maintain complete buoyancy will be recorded. The EchoMRI, grip strength meter and beaker/weight will be sterilized prior to use to ensure that germ-free conditions at the HDDC are maintained. Because [name] has previously measured lean mass and physical function in mice^[42, 43], he will perform these measurements at the HDDC.

Differences for the change in lean mass and physical function will be calculated relative to initial values. Statistical significance for the change in lean mass and physical function will be compared in mice colonized with fecal bacteria from HF or LF human donors and for germ-free mice that were not colonized with human gut bacteria with use of two-way ANOVA^[38].

III.2.c Bacterial taxa identification and association with the change in lean mass and physical function in mice colonized with human gut bacteria: Fecal pellets will be obtained from 5 germ-free mice at baseline, which will not be colonized with human gut bacteria. Five weeks post-colonization with human gut bacteria, fecal pellets will be collected from 60 mice (30 each from the HF and LF donors) and from the 5 germ-free mice that did not receive human gut bacteria. 16S rRNA gene profiling on these 70 fecal pellets will be performed as described in **Section III.1.a**.

Associations between gut bacteria-containing principal components and individual bacterial taxa with the 35-day change in lean mass, mouse grip strength and endurance capacity will be identified as described in **Section III.1.b**. Supervised machine learning (random forest) will be used to predict whether a sample came from a mouse colonized with HF or LF donor microbiota^[44].

The gut bacterial profile that is associated with the change in lean mass and physical function in mice colonized with HF or LF human fecal bacteria is expected to be similar to the gut bacterial profile that is associated with differentiation of HF from LF older adults. CIA will be used to identify associations between circulating metabolites with gut bacteria that collectively differentiate mice colonized with HF or LF gut bacteria.

A. Subject Characteristics

1) Subject eligibility criteria:

a) Inclusion criteria:

- i) Willing and able to sign the IRB approved informed consent form
- ii) Male and Female: males, 70-85y; females, 70-80y

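### ANOSIM is the test of overall HF-versus-LF gut profile, with no dispersion check, so a significant result cannot be read as a shift in composition

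*Protocol*

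**What the plan says.** In the Protocol, section I, under *Bacterial taxa that differentiate HF from LF older adults*, "Principal co-ordinate analysis (PCoA) of the phylogeny based Unifrac distance metric" is what "will be used to determine if the overall gut microbial profile in HF is significantly different when compared with LF older adults". An ordination gives no p-value, so the plan assigns significance to "The analysis of similarities function in the statistical software package PRIMER 6", at p ≤ 0.05. The SAP repeats this under the same heading. Neither document says whether UniFrac is weighted or unweighted.

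The other analyses near this test answer different questions. LEfSe works taxon by taxon: "To identify bacterial taxa and relative abundance that are significantly different in HF when compared with LF older adults". The random forest is for mouse samples and "will be used to predict whether a sample came from a mouse colonized with HF or LF donor microbiota". On allocation, section I states that the HF and LF "groups will each contain 20 subjects (10 men, 10 women".

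In the text available, neither document plans PERMANOVA, a test of homogeneity of multivariate dispersion, or a rule for telling a shift in composition from a difference in spread. Protocol section III.2.c refers to a Section III.1.b for component and taxon associations. No section with that label appears, so it could not be checked for further tests.

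**The concern.** ANOSIM ranks all pairwise distances and asks whether between-group ranks are higher on average than within-group ranks. If one group is more scattered, its members lie far from each other and also far from the tight group. The between-group ranks can then exceed the within-group ranks although both groups are centred on the same profile.

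The tempting reassurance is that equal group sizes protect against this. They protect PERMANOVA, for the reason shown in the working, but not a rank statistic.

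What is at stake is the scientific statement. That LF guts have a different composition, and that LF guts are more variable around the same composition, are different findings. As planned, p ≤ 0.05 would be reported as a different overall profile with no means of saying which finding it is. If the same test is used at 1 month, agreement with baseline would not settle the matter, because a difference in spread between the same participants could recur.

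**Working it through.** **The plan's own figure.** The documents give no operating characteristic for ANOSIM. The only power figure is for one taxon group, whose means and SDs (26.3 ± 13.2 and 14.8 ± 15.1) "yield an effect size of 0.81, a value that is sufficient to obtain 80% power at a type-I error probability of 0.05". Check: pooled SD = √((13.2² + 15.1²)/2) = √201.125 = 14.18, and 11.5/14.18 = 0.81. At 20 per group a t-test has 80.8% power one-sided and 70.5% two-sided, so the 80% reproduces as a one-sided figure. Sidedness is a separate matter. What is used here is the ratio of the two SDs, 15.1/13.2 = 1.14, the only spread comparison between function groups in the documents.

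**Why balance protects PERMANOVA but not ANOSIM.** With N = 40 there are 40 × 39/2 = 780 pairs: 190 + 190 = 380 within groups and 20 × 20 = 400 between.

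- Let the groups share a centre in *p* dimensions, with per-coordinate SDs σ₁ and σ₂. Expected squared distances are 2pσ₁² and 2pσ₂² within groups and p(σ₁² + σ₂²) between.
- With 190 pairs in each group, the average within-group value is also p(σ₁² + σ₂²). The contrast in squared distances, which PERMANOVA uses, is zero in expectation.
- ANOSIM uses R = (mean between rank − mean within rank)/(780/2). Ranking compresses the large distances, so averaging a small and a large within-group set tends to fall below the intermediate between-group set, and R becomes positive.
- The effect is not monotone. If the three sets separate completely, tight-group pairs take ranks 1-190, between-group pairs 191-590 and wide-group pairs 591-780. The within mean is (95.5 + 685.5)/2 = 390.5, the between mean is also 390.5, and R returns to 0.

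**Simulation with identical centroids.** Gaussian coordinates, Euclidean distance, 20 + 20, 499 label permutations, 1,000 data sets per cell. The spread ratios are assumptions. Entries are the percentage with p ≤ 0.05, ANOSIM first and PERMANOVA in brackets.

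| Dimensions | ratio 1 | 1.25 | 1.5 | 2 | 3 |
|---|---|---|---|---|---|
| 2 | 4.8 (4.8) | 7.9 (4.2) | 27.5 (5.8) | 76.8 (4.2) | 99.4 (5.2) |
| 5 | 5.6 (4.4) | 15.2 (5.2) | 54.7 (5.5) | 99.1 (4.4) | 100 (5.6) |
| 10 | 5.2 (4.9) | 20.5 (4.9) | 81.3 (4.6) | 100 (7.3) | 100 (4.6) |
| 50 | 5.2 (4.7) | 61.7 (4.3) | 99.7 (5.1) | 94.7 (5.2) | 36.2 (4.3) |

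Repeat runs agree to within simulation error and give 26% to 100% at ratio 1.5. At ratio 1.14, one run gave ANOSIM rejection of 4%, 10% and 18% in 2, 10 and 50 dimensions, and another gave about 7-21%.

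**Simulation on UniFrac.** A random 60-tip tree; Dirichlet groups share a mean composition and logistic-normal groups share a log-scale centre. Entries are percentages with p ≤ 0.05.

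| Model | Test and metric | ratio 1 | 1.25 | 1.5 | 2 |
|---|---|---|---|---|---|
| Dirichlet | ANOSIM, weighted | 4.4 | 13.4 | 58.4 | 100 |
| Dirichlet | PERMANOVA, weighted | 5.0 | 4.6 | 8.3 | 30.7 |
| Dirichlet | ANOSIM, unweighted | 5.1 | 36.6 | 97.7 | 100 |
| Logistic-normal | ANOSIM, weighted | 4.9 | 16.1 | 56.4 | 98.1 |
| Logistic-normal | PERMANOVA, weighted | 5.4 | 4.9 | 7.6 | 23.5 |
| Logistic-normal | ANOSIM, unweighted | 4.7 | 9.7 | 52.6 | 99.9 |

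PERMANOVA was not run on unweighted UniFrac.

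**The case against.** **ANOSIM is valid for its own null.** Its permutation null is that the groups are exchangeable. A difference in spread violates that null, so rejecting is not a false positive in that sense, and with equal spreads the test holds about 5%. The plan asks whether overall profiles differ and does not say centroid. This stands: a reader might infer that the Type I error is inflated, and the documents do not support that. The defect is one of interpretation.

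**The spread ratio is unknown.** This also stands. The one documented anchor, 1.14, comes from a single taxon group and lies where the effect is small to modest. A reader might infer that LF must be more heterogeneous because it spans SPPB 4 to 8 while HF can only score 11 or 12. That is spread in the selection variable, and nothing in the documents ties it to spread in UniFrac space. Matching on age, sex and BMI and the gastrointestinal and antibiotic exclusions may limit heterogeneity in both groups. None of this shows that the spreads are equal, and the plan has no check.

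**PERMANOVA is not immune.** Correct. It reached 24-31% on weighted UniFrac at ratio 2, where the centroid in distance space may itself move slightly. ANOSIM rejected 98-100% in the same cells. PERMANOVA therefore cannot be the sole basis for claiming a shift.

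**The importance of this test can be overstated.** A reader might take it as the headline test of Aim 1. No primary test is named, the sample size rests on one taxon group, and the study describes itself as a pilot.

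**Conclusion.** The concern holds as a limit on interpretation. With 20 per group, a shared centre and a difference only in spread, ANOSIM can reject well above 5%. Under Gaussian coordinates and Euclidean distance in 2 to 50 dimensions, the range is about 4-21% at a spread ratio of 1.14, 8-62% at 1.25 and 26-100% at 1.5, with PERMANOVA near 5% throughout. In the UniFrac models the corresponding ANOSIM ranges are 10-37% at 1.25 and 53-98% at 1.5.

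The ratios are assumed, so these figures show what could happen, not what will. They also do not mean that ANOSIM always rejects when spreads differ: in 50 dimensions rejection fell to 36% at ratio 3. The firm conclusion is that p ≤ 0.05 from the planned test cannot by itself support a claim of different composition, and equal group sizes do not change that.

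**What to change.** In the SAP paragraph on taxa that differentiate HF from LF, and in the matching Protocol paragraph:

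- Make PERMANOVA on the same UniFrac matrix the between-group test, and state whether UniFrac is weighted or unweighted.
- Report a permutation test of multivariate dispersion beside it, with each group's average distance to its centroid. With 20 per group, a non-significant dispersion test alone is weak evidence of equal spread, so say in advance how a material difference will be judged.
- Claim a compositional shift when PERMANOVA is significant and dispersion does not differ materially. If dispersion differs, state that spread may contribute and read the result with the PCoA plot. Describe a dispersion-only result as greater heterogeneity.
- Keep PCoA as the display. ANOSIM may stay as a secondary result.

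The cost is a few sentences and one routine extra analysis on a matrix that will exist anyway. No new data are needed. The downside is fewer significant results when only spread differs.

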- iii) BMI: males < 35, females <30 kg/m²
- iv) Willing to come to the HNRCA laboratory for baseline and 1-month follow-up study visits
- v) SPPB ≥ 11 (“High-Functioning”, HF; 20 subjects: 10 males, 10 females)
- vi) 4 ≤ SPPB ≤ 8 (“Low-Functioning”, LF; 20 subjects: 10 males, 10 females)

b) Exclusion Criteria:

- i) Non-English speaker
- ii) Acute or terminal illness
- iii) Surgery in the past 6 months
- iv) Lower extremity fracture within the past 6 months
- v) Myocardial infarction in the past 6 months
- vi) Coronary artery disease, peripheral vascular disease, previous stroke, or history of transient ischemic attacks
- vii) Cognitive impairment (MMSE score < 23)
- viii) Uncontrolled hypertension (> 160/100 mmHg)
- ix) Neuromuscular disease or drugs affecting neuromuscular function
- x) Androgen therapy in males
- xi) Estrogen therapy in females

- xii) Significant immune disorder
- xiii) Kidney Failure
- xiv) Pancreatic disease
- xv) Diabetes
- xvi) Gastrointestinal or malabsorption diseases
- xvii) History of cholecystectomy
- xviii) Use of probiotics, prebiotics or antibiotics in the past 3 months
- xix) The subject has any other condition, which in the opinion of the Investigator, precludes the subject's participation in the trial.
- xx) With the goal of matching the HF and LF groups for age, sex, and BMI, subjects may be excluded because their age, sex or BMI puts them outside the range needed for this study.

c) **Withdrawal/Termination criteria:** Subjects may stop participating in this study at any time for any reason. If an enrolled subject decides to withdraw from this research study, they will be asked to inform the Principal Investigator ([name]), the Lab Director ([name]), or his representative. The principal investigator may stop participation in this research study without the subject's permission for any of the following reasons:

- The participant did not adhere to any or all HNRCA volunteer rules and regulations
- Participant does not follow the study procedures
- There has been a change in the subject's health that would make the subject ineligible

B. Risk/benefit assessment:

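### The HF/LF ANOSIM does not use the fixed 10/10 sex split; if its permutations are unrestricted, the test is conservative whenever sex matters

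*Protocol*

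**What the plan says.** The protocol (I. Research Plan) and the SAP (I. Research Plan, Including Statistical Analysis) carry the same text on this point.

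- **Design.** Both state that "sex and BMI are associated with gut microbiome composition". To reduce microbial variability, the investigator writes "I propose to recruit HF and LF subjects that are matched for age, sex and BMI". The HF and LF "groups will each contain 20 subjects (10 men, 10 women").
- **Test.** In the paragraph on bacterial taxa that differentiate HF from LF older adults, the overall profile is examined by principal co-ordinate analysis of UniFrac distances. Then "The analysis of similarities function in the statistical software package PRIMER 6" "will be used to determine between-group statistical significance", with a threshold of p ≤ 0.05.
- **What is left open.** Neither document says whether the ANOSIM is one-way or two-way, whether sex is a block, or how labels are permuted. Sex is not a factor in any analysis described for the human comparison, and no size is given for the sex effect.
- **Eligibility (protocol, section A).** Limits differ by sex: "Male and Female: males, 70-85y; females, 70-80y" and "BMI: males < 35, females <30 kg/m²".

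**The concern.** A permutation test should relabel subjects only in ways the design could have produced. Here the quota allows only labellings with 10 men and 10 women in each group. Unrestricted permutation also generates labellings in which one group is mostly men and the other mostly women. If sex affects composition, as the plan says it does, those labellings bring sex variation into the null distribution that the observed labelling cannot contain. The p-value is then too large.

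This ANOSIM is the plan's only formal test of the overall HF/LF profile, and it has 40 subjects. Recruitment removes sex differences between the groups, but the analysis as written does not say that it will use this.

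**Working it through.** **1. The plan's own power figure.** No power is stated for the ANOSIM. The only human figure is 80% at N = 40 for a difference of 26.3 (SD 13.2) v 14.8 (SD 15.1) in one taxon.
- Pooled SD = √((13.2² + 15.1²)/2) = 14.18, so d = 11.5/14.18 = 0.81, as stated.
- With 20 per group, a t-test has 80.8% power one-sided and 70.4-70.5% two-sided. The 80% therefore reproduces one-sided.
- It concerns one mean, so it neither supports nor contradicts anything about the ANOSIM.

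**2. How many free relabellings keep the split.** Let k be the number of men labelled HF, and j = k − 10.
- P(j = 0) = C(20,10)²/C(40,20) = 184,756²/137,846,528,820 = 24.8%. The other 75.2% break the 10/10 split.
- P(j = ±1) = 2 × 167,960²/137,846,528,820 = 40.9%, so 34.3% have |j| ≥ 2.
- Within-sex relabellings number 184,756² = 3.4 × 10¹⁰, so the smallest attainable p-value is not a constraint.

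**3. Why the direction follows from the design.** The 40 subjects give 780 pairs: 400 between groups and 380 within groups.
- Cross-sex pairs among the 400 between-group pairs: k² + (20 − k)² = 200 + 2j².
- Cross-sex pairs among the 380 within-group pairs: 2k(20 − k) = 200 − 2j².
- Suppose cross-sex pairs have a mean distance rank δ above same-sex pairs. The mean between-group rank minus the mean within-group rank, which is the numerator of R, then contains δ[(200 + 2j²)/400 − (200 − 2j²)/380] = δ(−0.0263 + 0.01026 j²).

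This term is lowest at j = 0, where the observed labelling must lie, and rises with imbalance: −0.0160δ at j = ±1 and +0.0147δ at j = ±2. Whenever δ > 0, free permutation compares the observed R with values that sex has pushed upward. Within-sex permutation holds j at 0, so the term is the same for every relabelling.

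**4. Size, by simulation.** The documents give no sex share of variation, so it is **assumed** over 0-20%. The HF/LF effect is **assumed** at 4.5% of variation, chosen to give about 80% power. Other settings were 10 subjects per sex per group, Gaussian data on 10 axes, ranked Euclidean distances, 499 permutations, α = 0.05 and 10,000 runs per cell. The Monte Carlo standard error is about 0.4 points for power near 80% (√(0.8 × 0.2/10,000)).

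| Sex share | Type I error, free | Type I error, within-sex | Power, free | Power, within-sex, same R | Loss (points) | Power, R averaged over sexes |
|---|---|---|---|---|---|---|
| 0% | 4.9% | 4.9% | 82.8% | 82.7% | −0.1 | 67.9% |
| 1% | 4.4% | 4.8% | 81.9% | 82.3% | 0.4 | 67.7% |
| 2% | 4.4% | 5.1% | 81.5% | 83.0% | 1.5 | 68.3% |
| 5% | 4.0% | 5.2% | 79.4% | 82.9% | 3.5 | 68.0% |
| 10% | 2.3% | 4.9% | 73.4% | 82.1% | 8.7 | 67.8% |
| 20% | 0.8% | 5.2% | 57.2% | 81.6% | 24.4 | 68.3% |

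A separate 10-axis run (1,500 runs per cell) gave power of 83 v 82% (free v within-sex) at a 0% share, 83 v 84% at 2%, 81 v 85% at 5% and 79 v 88% at 10%. Checks on 5 and 20 axes (1,500 runs per cell) went the same way, with free type I error of 2.5% and 1.3% at a 10% share.

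**5. Why averaging R over the sexes is not equivalent.** That statistic uses only same-sex pairs, 2 × 190 = 380 of the 780, and drops the 400 cross-sex pairs. Its type I error was correct (4.8-5.2%), but its power was below that of free permutation until the sex share lay somewhere between 10% and 20%.

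**The case against.** **The plan does not say that it permutes freely.** This is correct. A reader might infer that the documents specify a one-way test with unrestricted permutation. They name only the function, the software and the threshold, so the loss is conditional on how the test is run. The layout still needs stating: at a 10% sex share the three possible versions have power of 73%, 82% and 68%, and leaving the choice open allows it to be made after the results are seen.

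**The loss may be trivial.** This also stands in part. The plan says that sex matters but not by how much. At shares up to 2% the loss is under 2 points. The 9-point loss needs sex to explain about twice as much variation as the assumed HF/LF effect (10% v 4.5%), and nothing in the documents establishes that. The sex-specific age and BMI limits could widen the difference between the sexes, but by an unknown amount. The sizes also depend on the number of axes: a 30-axis setting gave larger gaps, which should not be relied on. None of the simulations used UniFrac distances.

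**A conservative test does no harm to validity.** This is correct. A reader might infer that a significant ANOSIM would be untrustworthy, but the error runs the other way. The study calls itself a pilot, and no stated power figure is contradicted.

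**Stratifying is not automatically free.** This is correct as well. A team told only to stratify by sex might average R within sex and lose more power than it gained. The recommendation has to name the statistic as well as the permutation scheme.

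**Conclusion.** The point holds as a conditional one. The design fixes the sex split, and the ANOSIM text neither names a sex stratum nor restricts permutations. Run as an ordinary one-way test with free permutation, it would be conservative whenever cross-sex distances tend to be larger than same-sex distances. That direction follows from the pair counts and does not depend on the simulation.

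The size does depend on assumptions: a sex share that the documents do not give, an HF/LF effect of 4.5% of variation, and 10 Gaussian axes with Euclidean distances. On those terms the power loss is about 0-2 points at a 0-2% share, about 4 at 5% and about 9 at 10%. Type I error is about 4% at a 5% share and 2.3% at 10%. Within-sex permutation of the same R shows no measurable loss when sex has no effect.

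The documents do not support calling this a certain or large loss, or a threat to a positive finding. It is an inexpensive gain in precision and pre-specification that lowers the risk of missing a real difference.

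**What to change.** In the paragraph on bacterial taxa that differentiate HF from LF, in both the protocol and the SAP, add a sentence such as:

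> *HF and LF will be compared with the one-way ANOSIM R computed on UniFrac distances among all subjects; its p-value will be obtained by permuting HF/LF labels separately among men (10 v 10) and among women (10 v 10).*

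State also that a two-way ANOSIM averaging R within sex will not be used for this comparison. If the final counts differ from 10 per cell, permute within each sex using the observed counts.

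The change needs no new data or subjects. The one practical cost is that the UniFrac matrix may have to be exported to other software if the named package cannot restrict permutations for this statistic.

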Transplantation of gut microbiota from a healthy human adult into germ-free mice resulted in all bacterial phyla, 92% of bacterial classes and 88% of genus-level taxa being detected in the feces of recipient germ-free mice^[37]. Human gut bacteria-containing mice fed a high-fat western diet gained significantly more adiposity during the two weeks following transplantation than mice that consumed a low-fat, plant polysaccharide-rich diet^[37], evidence that demonstrates a causative role for diet-induced increases in adiposity by human gut bacteria. Similarly, transplantation of human gut microbiota from 3 twins (2 female and 1 male) discordant for obesity into germ-free mice resulted in ~75% of family-level bacterial taxa and 99.7% of the functions encoded by the donor's microbiome being represented in recipient mice, thereby resulting in a greater increase in adiposity in mice colonized with fecal microbiota from obese, when compared with its lean co-twin^[38].

Collectively, these studies demonstrate that transfer of gut bacteria from humans into germ-free mice is highly efficient, functions encoded by the transferred microbiome are maintained, and phenotypes are transmissible. The objective of **AIM 2** is to test the causative role of human gut bacteria on the maintenance of lean mass and physical function by transferring fecal microbiota from HF and LF older adults into germ-free mice.

Statistical Power: Germ-free mice colonized with fecal bacteria from obese humans gained significantly more adiposity than germ-free mice colonized with fecal bacteria from their lean co-twin ($10.0\% \pm 5.0\%$ compared with $0.1\% \pm 2.0\%$), a result that was significant 15 days after colonization^[38]. Based on these data, the resulting effect size of 2.6 is sufficient to obtain 99% power at a type-I error probability of 0.05 with a sample size of 12 human subjects. Accordingly, with the goal of identifying a similar change in lean mass and physical function, I propose to transfer fecal bacteria from 12 older adults into germ-free mice.

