III.2.a Colonization of germ-free mice with human gut bacteria from HF and LF older adults: Fecal samples from 6 HF (3 males, 3 females) and 6 LF (3 males, 3 females) older adults will be transferred into sex-matched (with the goal of minimizing sex-associated gut microbial variability^[6, 7]) C57BL/6J germ-free mice for a duration of 5 weeks at the Germ-Free and Gnotobiotic Microbiology Core at the Harvard Digestive Disease Center (HDDC; Boston, MA). The transmissible effect of host phenotype by gut microbiota has been previously reported by transferring human fecal bacteria into C57BL/6J germ-free mice^[36-38]. Furthermore, the homogenous genetic background provided by inbred C57BL/6J germ-free mice allows for a cleaner system to dissect signals from gut bacteria-host interactions, and improves experimental reproducibility, when compared with genetically heterogeneous GFM^[39]. One fecal sample from each human donor will be transferred into 5 separate germ-free mice (based on the range of germ-free mice used in human fecal transfer experiments^[36, 38]), resulting in 60 mice colonized with human gut microbiota. 5 germ-free mice will not be colonized with fecal bacteria from older adults (germ-free control group). All recipient mice will be fed *ad libitum* with a commercial, sterilized mouse chow^[38]. Food consumption will be measured daily to ensure that changes in lean mass or physical function do not result because of differences in food intake.

III.2.b Measurement and analysis of the change in lean mass and physical function in mice colonized with human gut bacteria: Lean mass and physical function in mice colonized with human gut bacteria will be measured on day 0 (prior to colonization), 9, 18, 27 and 35 days post-colonization at the HDDC. Lean mass will be measured with use of quantitative magnetic resonance imaging (EchoMRI-3in1 instrument, Houston, TX)^[38]. Muscle strength will be measured using a grip strength meter for mice (Technical and Scientific Equipment GmbH, Bad Homburg, Germany)^[40]. Each mouse will firmly grab the pulling bar of the grip strength meter with both forepaws and then pulled gently backwards until it releases its grip. The peak force of each trial is considered the grip strength. A 1-liter beaker filled with water will be used as a swimming pool to test endurance capacity^[41].

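### The mouse experiment specifies no masking to donor group, so one operator's expectation could create or inflate an HF-LF difference in grip strength and swim time

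*Protocol*

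**What the plan says.** Aim 2 is the causal part of the project. Its objective is to "test the causative role of human gut bacteria on the maintenance of lean mass and physical function by transferring" stool from HF and LF donors into germ-free mice. Section III.2.a uses 6 HF and 6 LF donors: "One fecal sample from each human donor will be transferred into 5 separate germ-free mice". That makes 30 mice per group, plus 5 uncolonized controls.

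Section III.2.b sets three outcomes, measured on day 0 before colonization and on days 9, 18, 27 and 35:

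- **Lean mass.** "Lean mass will be measured with use of quantitative magnetic resonance imaging", which is an instrument reading.
- **Grip strength.** The mouse holds a bar and is "then pulled gently backwards until it releases its grip". The score is defined as follows: "The peak force of each trial is considered the grip strength". The number of trials, and which one counts, are not given.
- **Swimming endurance.** "The amount of time that the mouse is able to maintain complete buoyancy will be recorded". No objective end criterion is given.

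One person is named for all of this because of prior experience with such measurements: "he will perform these measurements at the HDDC". Change from day 0 is compared by two-way ANOVA. The SAP repeats the whole section. Neither document mentions masking, coded cages, test order, a second reader, or how mice are assigned to donors.

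**The concern.** In grip testing, the speed and angle of the pull belong to the tester. In the swim test, the tester decides when buoyancy is lost. If the tester knows which mice carry HF or LF microbiota, an expectation about the result can enter the reading without any intent.

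Aim 1 is associational, so the causal claim rests on Aim 2. The plan protects Aim 2 against several other threats, through sex matching, inbred mice, daily food intake and day-0 values. It does not address this one. Change from day 0 does not help, because day 0 comes before colonization: bias in the readings from day 9 to day 35 passes straight into the change score. A constant shift between groups looks the same as a treatment effect, and no later analysis can separate the two.

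**Working it through.** **The plan's own figure.** The only stated figure for this experiment is 99% power with 12 donors, an effect size of 2.6 and a type-I error of 0.05 (Aim 2, Statistical Power). The effect size is (10.0 − 0.1)/√((5.0² + 2.0²)/2) = 9.9/3.808 = 2.60. With 6 per group, power is 98.1% two-sided and 99.4% one-sided by the noncentral t, and 99.5% and 99.8% by the normal approximation. The figure reproduces and is not in dispute. It concerns adiposity gain, so it gives no SD for grip or swim time.

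**What the illustration assumes.** The documents give no size for operator bias. I assume no true HF-LF effect, a constant spurious shift b of 0.25 or 0.5 in units of the between-mouse SD, and a two-sided t-test at 0.05. The group sizes come from III.2.a. The test is a simplification of the planned two-way ANOVA.

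**Mice as the unit, 30 vs 30, treated as independent.** The noncentrality is b × √(30/2), with 58 degrees of freedom and a critical value of 2.002.

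- b = 0.25: noncentrality 0.968, rejection 15.9%
- b = 0.5: noncentrality 1.936, rejection 47.8%

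**Donor means as the unit, 6 vs 6, 5 mice each.** With within-donor correlation r, the SD of a donor mean is f = √((1 + 4r)/5) mouse SDs. The noncentrality is (b/f) × √(6/2), with 10 degrees of freedom and a critical value of 2.228.

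| r | f | b = 0.25 | b = 0.5 |
|---|---|---|---|
| 0 | 0.447 | 14.2% | 41.7% |
| 0.2 | 0.600 | 10.0% | 25.7% |
| 0.5 | 0.775 | 8.0% | 17.3% |
| 0.8 | 0.917 | 7.1% | 13.7% |
| 1 | 1.000 | 6.8% | 12.3% |

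All rejection rates count both tails. The nominal rate is 5%.

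**The case against.** The strongest reply is that the documents are silent rather than wrong. A reader might infer that the operator will be unmasked and will see cage labels, but the text mentions neither labels nor who knows the donor group. A reader might also infer that the operator holds the study hypothesis. The name is removed, and the stated reason for the choice is experience. Section III.2.c does record an expected result, but it concerns the bacterial profile, not grip or swim time. These limits stand: the supportable statement is that no masking is specified.

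A second reply concerns scope. Lean mass is read by EchoMRI, and the 16S and random-forest analyses do not depend on handling. It would be too strong to say that Aim 2 as a whole is biased.

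Third, the size is assumed throughout. The mouse-level rates also have 5% as their baseline only if mice from one donor are independent. With r of 0.2 or 0.5 and no operator bias at all, a normal approximation already gives P(|Z| > 1.96/√1.8) ≈ 14% or P(|Z| > 1.96/√3) ≈ 26%. That excess is a clustering problem and should not be charged to masking. The donor-level table is free of it.

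Fourth, inbred mice, sex matching and day-0 values already limit baseline imbalance, so random allocation is the lesser part of the point. Sterilizing equipment between animals may also make a fully random test order costly. Both are fair. Neither answers the absence of masking for two operator-dependent outcomes.

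**Conclusion.** The point holds for grip strength and swim time. One operator takes all readings, both outcomes depend on handling or judgement, and the plan followed as written contains no safeguard for the HF-LF contrast. Expectation could create or inflate a difference; the documents do not show that it will.

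The size cannot be derived from the documents. Under an assumed shift of 0.25 to 0.5 mouse SD with no true effect, two-sided rejection is 16% to 48% for 30 vs 30 independent mice. For 6 vs 6 donor means it is 7% to 14% at 0.25 SD and 12% to 42% at 0.5 SD, as within-donor correlation falls from 1 to 0. These rates illustrate the mechanism and are not estimates of the error in this study. This should be corrected, because the safeguard is cheap and the bias cannot be removed afterwards.

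**What to change.** In section III.2.b of both documents, state that the gnotobiotic core will:

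- allocate mice to donors at random within sex;
- code cages and mice so that the operator cannot tell HF-donor from LF-donor animals;
- hold the key until the day-35 data are locked;
- set the test order at random on each measurement day, as far as isolator and sterilization logistics allow (for example, by cage).

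The same operator can still take every measurement, and no extra animals or staff are needed. If masking is already intended, stating it in III.2.b settles that part.

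The cost is some work on coding and possibly extra decontamination steps when the order mixes animals from different donors. The germ-free controls may remain recognisable from their housing, so masking can be assured only for HF versus LF, which is the contrast that matters here.
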